5.3.3.3. Combined unique active lesions (CUAL)

The following variables are derived per subject for CUAL:

- Total number of CUAL derived as the number of new or enlarging T2 lesions at each scheduled scan* within the Analysis Period, plus the number of T1 Gd + lesions at each corresponding scheduled scan within the Analysis Period where new or enlarging T2 lesions were measured (AP3), and corresponding number categorized (0, >0** 5, >5 10, >10 15, >15 20, >20 25, >25)
- Cumulative number of CUAL over the Analysis Period, derived as the sum of all new or enlarging T2 lesions at each scheduled scan* within the Analysis Period, plus the number of T1 Gd + lesions at each corresponding scheduled scan within the Analysis Period where new or enlarging T2 lesions were measured (AP3);
- Cumulative number of CUAL over the Analysis Period as derived above, categorized into the following categories: 0, 1-5, 6-10, 11-15, 16-20, 21-25, 26-30, 31-35, 36-40 and 41+ (AP3).

* Excluding T1 Gd+ lesions measured at the core scheduled visits at Week 4, 8, 16 and 20. This restriction is necessary to avoid double-counting lesions when the MRI scans are less than 12 weeks apart, as only total (new + persisting) T1 Gd+ lesions are collected, but the derivation of CUAL should consider only new T1 Gd+ lesions. As T1 Gd+ lesions are assumed not to enhance for more than 12 weeks, it is assumed that the number of T1 Gd+ lesions counted when the scans are at least 12 weeks apart is equivalent to the number of new T1 Gd+ lesions.

** Fractional values are possible and reflect allocation of T2 lesions proportionally to adjacent time-windows.

5.3.3.4. Brain volume

The following variables are derived per subject brain volume:

• Percentage change from ponesimod baseline* in brain volume per MRI timepoint (as defined in Table 8 above) in AP3.

* Percentage change in brain volume from Visit 2 of the core study, and percentage change in brain volume from Visit 11 of the core study are derived by MIAC and provided in SDTM. Percentage change from ponesimod baseline per scan is derived in the ADaM dataset as follows:

- For subjects randomized to ponesimod in the core study, percentage change in brain volume from ponesimod baseline is equal to percentage change in brain volume from Visit 2 of the core study (PBVC in the core study SDTM, PBVC_V2 in the extension study SDTM).
- For subjects randomized to placebo in the core study and continuing to the extension study, percentage change in brain volume from ponesimod baseline is equal to percentage change in brain volume from Visit 11 of the core study (PBVC_V11).

5.3.4. Analysis of MRI-related variables

5.3.4.1. T1 Gd + lesions

The cumulative total number of T1 Gd+ lesions is analyzed for AP3 on the PAS, according to the NB model described in Section 6.12.1. The model includes the cumulative total number of T1 Gd+ lesions in the Analysis Period for each subject as the response variable (as defined in

Section 5.3.3.1), treatment as a factor and the logarithm of the number of MRI timepoints in the Analysis Period (years) (as defined in Section 5.3.3.1) as an offset variable. This analysis was conducted for the Interim Analysis CSR and is not planned to be conducted for the Final CSR.

Mean model-based estimates of the total number of T1 Gd+ lesions by treatment, as well corresponding 95% CIs are presented, as well as rate ratios and 95% CIs for the comparisons between doses. This sensitivity analysis was conducted for the Interim Analysis CSR and is not planned to be conducted for the Final CSR.

As a sensitivity analysis, the cumulative total number of T1 Gd+ lesions is analyzed as described above, also including the additional baseline covariates included for the sensitivity analysis of ARR as described in Section 5.3.2.3. This sensitivity analysis was conducted for the Interim Analysis CSR and is not planned to be conducted for the Final CSR.

The total number of T1 Gd + lesions per MRI timepoint and the total volume of T1 Gd+ lesions at each MRI timepoint (as defined in Section 5.3.3.1) are summarized descriptively by treatment group for AP3 on the PAS. These data are presented in both a table and a figure.

The number of subjects with no T1 Gd+ lesions (lesion-free) at each MRI timepoint is summarized by treatment group for AP3 on the PAS: frequency counts and percentages. The denominator for percentages is the number of subjects with an MRI scan at the timepoint.

All T1 Gd+ lesion and volume data are presented in a listing for AP3 on the PAS.

5.3.4.2. New or enlarging T2 lesions

The cumulative number of new or enlarging T2 lesions (as defined in Section 5.3.3.2) is analyzed separately for AP3 on the PAS, as described in Section 5.3.4.1 for the cumulative total number of T1 Gd+ lesions. The logarithm of the time up to the last MRI scan at which T2 was measured in the Analysis Period (years) is used as an offset variable. This analysis was conducted for the Interim CSR and is not planned to be conducted for the Final CSR.

The number of new or enlarging T2 lesions per MRI time window (as defined in Section 5.3.3.2) is summarized descriptively by treatment group as described in Section 5.3.4.1 for the cumulative number of T1 Gd+ lesions, and is presented in both a table and a figure for AP3 on the PAS.

The total T2 lesion volume per MRI timepoint and corresponding change from ponesimod baseline in total T2 lesion volume per MRI timepoint are summarized descriptively in the same way.

The number of subjects with no new or enlarging T2 lesions (lesion-free) in the Analysis Period is summarized by treatment group separately for AP3 on the PAS: frequency counts and percentages. The denominator for percentages is the number of subjects with at least one MRI scan at which T2 was measured during the Analysis Period.

All T2 lesion and volume data are presented in a listing for AP3 on the PAS.

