5.3 Efficacy endpoints

All statistical tests are of exploratory nature. No adjustment for multiple comparisons will be made.

Annualized relapse rate:

ARRs will be explored by means of negative binomial regression models.

Time to event data:

The time to event (e.g., first confirmed relapse) will be analyzed using the log-rank test. The Kaplan-Meier estimates at different time points will be provided together with the 95% two-sided confidence limits (CLs) calculated using Greenwood's formula for the estimate of the standard error. The time to event will be displayed by a Kaplan-Meier plot.

Patients free of relapse

The proportion of relapse free patients will be estimated by means of Kaplan-Meier method (time to first confirmed relapse).

MRI-related endpoints

Number of total T1 Gd+ lesions, number of combined unique active lesions, and number of new or enlarging T2 lesions will be analyzed by means of negative binomial regression models.

Methods for handling of missing data will be defined in the SAP for the individual endpoints as applicable.

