5.3.1.3. Time to first confirmed/any relapse up to end of the Analysis Period

Time to first confirmed release is derived for AP3 as follows:

The time to first confirmed relapse (in days) is defined as [Date of first confirmed relapse - ponesimod start date + 1] in days.

Subjects without any confirmed relapses during the Analysis Period are censored, and censored time is defined as the Analysis Period end date - ponesimod start date + 1, in days. In the listings censoring is displayed as 'End of Analysis Period' for subjects who did not have a relapse by the end of the Analysis Period. Relapses are labelled as either 'Confirmed Relapses' or 'Unconfirmed Relapses'.

The definition above is also applied for the derivation of time to first 'any' relapse for AP3, i.e., including confirmed and unconfirmed relapses.

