5.3.2.5. Time to first confirmed/any relapse up end of the Analysis Period

Time to first confirmed relapse is analyzed for AP3 on the PAS, using the Kaplan-Meier method and Cox proportional hazards model, as described in Section 6.12.2.1 and 6.12.2.2.

The reference time is the study day, i.e., days elapsed since start of treatment with ponesimod.

The results of the Kaplan-Meier analysis are summarized in a table including:

- Number of subjects at risk, with an event and censored, KM estimates (unstratified) and corresponding CI, at intervals of 48 weeks;
- Median, 25th and 75th percentiles of the survival function together with corresponding CIs.

The hazard ratio and corresponding 95% CI based on a Cox proportional hazards model including treatment as a factor are presented in a separate table for the following comparisons:

- ponesimod 20 mg vs. Ponesimod 10 mg;
- ponesimod 40 mg vs. Ponesimod 10 mg;
- ponesimod 40 mg vs. Ponesimod 20 mg.

The results of Kaplan-Meier analysis are also presented graphically, including the KM estimates and corresponding CIs at the time points specified above up to the timepoint where at least 10% of subjects in each group are still at risk, as well as the hazard ratios and CIs from the Cox proportional hazards model.

Time to first 'any' relapse (all relapses) is analyzed as described above for confirmed relapses.

As a sensitivity analysis, time to first confirmed relapse is analyzed as described above, with a stratified log-rank test as described in Section 6.12.2.1 to include the additional baseline covariates: number of documented relapses (≤ 1 and ≥ 2) in the past 24 months prior to core baseline, EDSS at ponesimod baseline (≤ 3.5 and > 3.5). This sensitivity analysis was conducted for the Interim Analysis CSR and will not be conducted for the Final CSR.

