5.3.2.6. Other relapse-related characteristics

Other relapse-related characteristics are summarized by treatment group separately for AP3 on the PAS. This includes the following:

- Number (%) of subjects with at least one: relapse, , relapse treated with corticosteroids; for all relapses up to end of the Analysis Period, confirmed relapses up to end of the Analysis Period.
- Number (%) of subjects without any (confirmed or total) relapse.
- Number (%) of relapses (out of total number of relapses) treated with corticosteroids and descriptive statistics for continuous data for relapse duration (days); for all relapses up to end of the Analysis Period as well as for confirmed relapses up to end of the Analysis Period.
- Number (%) of relapses classified as mild/moderate/severe; for all relapses up to end of the Analysis Period as well as for confirmed relapses up to end of the Analysis Period.
- Number of confirmed relapses, number of all relapses, ratio of confirmed vs. all relapses; for relapses up to end of the Analysis Period for all relapses up to end of the Analysis Period as well as for confirmed relapses up to end of the Analysis Period

As described in Section 5.3.1.5, relapses requiring hospitalization will not be included in the summaries.

A listing of all relapses including hospitalizations, administration of corticosteroids, severity of relapse will be presented.

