5.3.3.2. New or enlarging T2 lesions and T2 volume

For summaries of new or enlarging T2 lesions (T2New_R) over time, the number of lesions is assigned to the timepoint in which they fall, as defined in Table 9 below. As the number of new or enlarging lesions is always relative to the previous assessment, if the observation period for the scan crosses the boundary of a time window, the lesions are allotted **proportionally** to the time windows which they cross. For example, if a subject has a scan at Week 24, and the next scheduled scan occurs at Week 72, the Week 72 scan will count the number ("x") of new or enlarging T2 lesions since Week 24. In this case x/2 lesions would be allocated to the Week 0-48 window, and x/2 lesions would be allocated to the Week 48-96 window.

Time windows are derived from time since first administration of ponesimod according to the schedule defined in Table 9 below.

Time window displayed	Time window (weeks)
Week 0-48	0 - <48
Week 48-96	48 - <96
Week 96-144	96 - <144
Week 144-192	144 - <192
Week 192-240	192 - <240
Week 240-288	240 - <288
Week 288-336	288 - <336
Week 336-384	336 - <384
Week 384-432	384 - <432
Week 432-480	432 - <480
Week 480-528	480 - < 528
Week 528-576	528 - < 576
Week 576-624	576 - < 624
Week 624-672	624 - < 672
Week 672-720	672 - < 720

Table 9:	MRI time window	definition: scan	mapping for new o	r enlarging T2 lesions
----------	-----------------	------------------	-------------------	------------------------

The following variables are derived for T2 lesions per subject using the above time windows:

- Number of new or enlarging T2 lesions (T2New_R) per MRI time window (as derived in Table 9 above) in AP3;
- No new or enlarging T2 lesions during each MRI time window in AP3.

The following additional variables are derived for T2 lesions per subject: Only scheduled scans are considered, however premature EOT scans are included.

- Cumulative number of new or enlarging T2 lesions over Analysis Period (for AP3), derived as the sum of the number of new or enlarging T2 lesions at each scheduled scan during the Analysis Period;
- Absence of new or enlarging T2 lesions over the Analysis Period (for AP3), derived where the sum of the number of new or enlarging T2 lesions at each scheduled scan during the Analysis Period is zero;
- Time (years) from first administration of ponesimod to last MRI scan at which T2 was measured in the Analysis Period (for AP3). Only scheduled scans are used for this derivation.

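### The T2-lesion-free and zero-CUAL percentages over AP3 are crude proportions across very unequal follow-up, with no censoring-adjusted version planned

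*SAP*

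**What the plan says.** **T2.** SAP 5.3.3.2 treats a subject as T2-lesion-free over AP3 when the new or enlarging T2 lesions sum to zero over whichever scheduled scans exist, premature end-of-treatment scans included. SAP 5.3.4.2 then states: "The number of subjects with no new or enlarging T2 lesions (lesion-free) in the Analysis Period is summarized by treatment group". The display is counts and percentages, and "The denominator for percentages is the number of subjects with at least one MRI scan at which T2 was measured during the Analysis Period". No minimum follow-up applies. The negative binomial model for cumulative T2 lesions, which had log time as offset, is dropped: "This analysis was conducted for the Interim CSR and is not planned to be conducted for the Final CSR".

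**CUAL.** SAP 5.3.4.3 tabulates categories of the AP3 CUAL count, including zero, on the same denominator. The offset model is kept for CUAL.

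**AP3.** SAP 5.1.9 includes everyone with at least one ponesimod dose. The time-on-study categories in SAP 5.2.1.7 run from 6 months or less to more than 12 years.

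**Relapse.** SAP 5.3.2.6 lists "Number (%) of subjects without any (confirmed or total) relapse". SAP 5.3.2.5 also gives a Kaplan-Meier table: "Number of subjects at risk, with an event and censored, KM estimates (unstratified) and corresponding CI, at intervals of 48 weeks". Under SAP 5.3.1.3, "Subjects without any confirmed relapses during the Analysis Period are censored". Protocol 5.3 names the same method: "The proportion of relapse free patients will be estimated by means of Kaplan-Meier method (time to first confirmed relapse".

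**The concern.** A proportion free of an event over a period has a clear meaning only when everyone is observed for that period. Here the period ends at each subject's own last study date. The T2 figure mixes lesion-free probabilities at a few months with those at 12 years, weighted by whatever follow-up pattern arose. A subject who leaves before a first lesion stays in the numerator permanently.

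The AP3 percentage is likely to be read as the share of patients who stay free of new T2 lesions on long-term treatment. It does not estimate that share, and it moves with follow-up as well as with disease activity. For T2 nothing beside it corrects the reading: no time-to-event analysis is planned and the offset model is gone. The protocol's MRI endpoints (section 3.10.1) include patients without Gd+ lesions but not T2-lesion-free status, so there is no protocol method to fall back on.

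The SAP handles the T1 counterpart better. In 5.3.4.1, T1-lesion-free is shown at each MRI timepoint among subjects scanned then.

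**Working it through.** The plan states no lesion-free percentage, so there is no figure to reproduce. The check asks how far a crude proportion sits above the 12-year value under follow-up like this study's.

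**1. How uneven is follow-up?** Protocol 1.3.2.4 gives, for 20 mg at the March 2019 cut-off, a median exposure of 8.02 years and 817 subject-years. The group size is not stated. Protocol 1.3.2.3 has 464 randomized 1:1:1:1, so 464/4 = 116 per arm. Two subjects on 20 mg were not treated, leaving 114. Up to about 116/3 ≈ 39 placebo switchers bring the maximum to about 153. I take 130 to 153 as an assumed range.
- Mean exposure: 817/130 = 6.28 years; 817/153 = 5.34 years. Both are well below the median.
- If the longer-exposed half averages 8.5 years (assumed), the other half averages (817 − 65 × 8.5)/65 = 4.07 years, or (817 − 76.5 × 8.5)/76.5 = 2.18 years.

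**2. Lesion-free probability by follow-up.** For negative binomial counts with rate m per year and dispersion k, P(0 by t) = (1 + k·m·t)^(−1/k). No T2 rate is given for this study. I assume m = 0.5 to 1.405; the upper value is the Phase 3 CUAL rate for 20 mg in Protocol 1.3.2.3, a proxy only. Dispersion k = 2 to 4 is also assumed. For m = 0.5 and k = 2:
- leaving at 1 year: (1 + 1)^(−1/2) = 0.707
- followed to 12 years: (1 + 12)^(−1/2) = 0.277

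**3. Crude figure against the 12-year value.** The crude proportion is the mean of P(0) over subjects' own follow-up. The shorter-followed half is as in step 1, the other half reaches 11.5 to 12.6 years, subjects with under 0.4 years are excluded as unscanned, and drop-out is independent of lesions. Ranges are over N = 130 to 153.

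| m per year | k | Crude | 12-year value | Excess (points) |
|---|---|---|---|---|
| 0.5 | 2 | 37.2–41.2% | 27.7% | 9.5–13.5 |
| 0.5 | 4 | 51.8–54.7% | 44.7% | 7.1–10.0 |
| 1.0 | 2 | 27.8–31.5% | 20.0% | 7.8–11.5 |
| 1.0 | 4 | 44.2–46.9% | 37.8% | 6.4–9.1 |
| 1.405 | 2 | 24.0–27.3% | 17.0% | 7.0–10.3 |
| 1.405 | 4 | 40.8–43.4% | 34.8% | 6.0–8.6 |

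The excess is about 6 to 14 points. At N = 153 the fitted median was 7.68 rather than 8.02 years, so the top of the range is slightly generous.

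**4. Lighter drop-out.** Let a fraction d leave uniformly between 0.4 and 8 years and the rest reach 12 years. Then excess = d × (mean early P(0) − P(0 by 12)). For m = 0.5 and k = 2 the mean early value is (√9 − √1.4)/(0.5 × 7.6) = 0.478. With d = 0.1 the excess is 0.1 × (0.478 − 0.277) = 2.0 points; with d = 0.2 it is 4.0. For m = 1.405 and k = 4 the early mean is 0.476, giving 1.3 and 2.6 points. The direction is upward throughout; the size depends on drop-out.

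**The case against.** Everything in this SAP is exploratory, p-values were removed, and no test rests on these percentages. The T2 denominator is stated openly. T2 lesions per 48-week window are tabulated and plotted, exposure is reported, and the retained CUAL model, with its time offset, includes T2 lesions. Kaplan-Meier on roughly yearly scans ignores interval censoring and still assumes independent drop-out, so it is no gold standard. Drop-out after a first lesion does not inflate the figure at all.

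Most of this stands and limits the weight of the point. It does not remove it: lesion counts and rates are not a lesion-free proportion, and the per-window lesion-free variable derived in SAP 5.3.3.2 is not reported in 5.3.4.2.

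A reader might extend the criticism to relapse and infer an undeclared departure from the protocol. The documents do not support that. SAP 5.3.2.5 keeps Kaplan-Meier for confirmed and for any relapse in the Final CSR; only the stratified sensitivity analysis was dropped. Protocol 3.10.1 itself lists the number of patients without any relapse, so the crude count is a protocol endpoint.

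**Conclusion.** The point holds for T2-lesion-free and for zero CUAL. Both are crude percentages over unequal follow-up, biased upward relative to a fixed long horizon, with no censoring-adjusted counterpart. The 6 to 14 points were computed for T2 only. They rest on assumed lesion rates, dispersion, group size and follow-up shape, and on independent drop-out. With 10 to 20% drop-out under the same lesion assumptions, the excess is about 1 to 4 points.

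Two stronger readings are tempting. One is that the figures are grossly too favourable; the documents give neither drop-out rates nor event-free results, so this is not established. The other is that the percentages will create a false dose difference. Protocol 1.4.5 reports more dyspnea, peripheral edema and cough on 40 mg, so unequal discontinuation is possible, but no rates by arm are given.

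This is a worthwhile correction to descriptive reporting. It does not threaten any inferential claim.

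**What to change.** - **T2 and zero CUAL:** report the lesion-free proportion at 48-week steps with numbers at risk, by Kaplan-Meier or an interval-censored estimate. The event is the first scheduled scan with a lesion of the relevant type; censor at the last T2 scan.
- **Alternative for T2:** tabulate the per-window variable from SAP 5.3.3.2 among subjects scanned in that window, with numbers at risk. State the rule for scans spanning two windows, since proportional allocation can mark both as not lesion-free for one lesion.
- **Any AP3 crude percentage kept:** label it descriptive and show follow-up by arm beside it.
- **Relapse:** no new analysis. Quote the Kaplan-Meier estimates from SAP 5.3.2.5 as the relapse-free proportion and label the percentage in SAP 5.3.2.6 as descriptive.

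The cost is about one additional table from variables and methods largely in the SAP already. The reported figures would be somewhat less favourable.

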5.3.4.3. CUAL

The cumulative number of CUAL (as defined in Section 5.3.3.3) is analyzed for AP3 on the PAS, as described in Section 5.3.4.1 for the cumulative total number of T1 Gd+ lesions. The logarithm of the time up to the last MRI scan at which T2 was measured in the Analysis Period (years) is used as an offset variable.

The number of CUAL per MRI time window (as defined in Section 5.3.3.2) is summarized descriptively by treatment group, as described in Section 5.3.4.2 for the cumulative number of new or enlarging T2 lesions, and is presented in both a table and a figure for AP3 on the PAS.

Frequency counts and percentages for the categorical number of CUAL in the Analysis Period are presented by treatment group for AP3 on the PAS. The denominator for percentages is the number of subjects with at least one MRI scan at which T2 was measured during the Analysis Period.

All CUAL data is presented in a listing for AP3 on the PAS.

5.3.4.4. Brain volume

Descriptive statistics for percentage change from ponesimod baseline in brain volume by MRI timepoint are presented for AP3 on the PAS. Additionally, a line graph of percent change from baseline by MRI timepoint is presented.

All brain volume data is presented in a listing for AP3 on the PAS.

5.3.5. Neurological variables

EDSS and FS scores as assessed by the investigator are stored in SDTM.QS. The two QS datasets are concatenated for the purposes of this analysis.

5.3.5.1. Time to 24-week confirmed disability progression up to end of the Analysis Period

Time to 24-week confirmed disability accumulation from baseline is derived for AP3 using the ponesimod baseline.

Time to 24-week confirmed disability accumulation from baseline (the last non-missing measurement taken prior to first dose of ponesimod) up to end of the Analysis Period is derived based on the EDSS scores. Disability accumulation is defined as an increase of at least 1 point in the EDSS score if baseline EDSS was between 1 and 5.0, an increase of at least 1.5 points if baseline EDSS was 0, or an increase of at least 0.5 points if the baseline EDSS was equal or greater than 5.5.

A 24-week confirmed disability accumulation is defined as a 24-week sustained increase from baseline in the EDSS scores. i.e., every EDSS score (scheduled or unscheduled, with or without relapse) within a 24-week duration after the first accumulation should meet the accumulation criteria as specified above.

Data derivation for time to event analysis includes derivation of the event status and the time to event variables.

The steps to determine whether a subject has a 24-week confirmed disability accumulation or not (i.e., event status) and how the time to event variable is calculated are summarized in the numbered points below:

1. Detection of a disability accumulation onset:

All available post-baseline EDSS assessments (scheduled or unscheduled, with or without relapse) are compared to the baseline EDSS to assess if the change from baseline meets the disability accumulation criteria as described above. The disability accumulation onset date is the date of the first EDSS meeting the disability accumulation criteria.

2. Confirmation of a disability accumulation:

As a general rule, disability accumulation can only be confirmed at a scheduled visit and in the absence of a relapse. Note that the EOS/early discontinuation visit and the follow-up visit (in core, TP1, TP2, and TP3) are protocol specified visits and are treated as scheduled visits and thus can be used to confirm a disability accumulation if applicable. Specifically, the confirmation visit is the first scheduled visit meeting the following conditions.

- This visit is ≥ 24 weeks (140* days) from the potential onset date;
- The EDSS assessment is NOT performed during a relapse (between start and end date of a relapse, or if relapse end date is missing, then until start date of relapse + 90 days);
- All available EDSS scores (scheduled or unscheduled, with or without relapse) between the disability accumulation onset and this visit meet the disability accumulation criteria;
- The EDSS confirmation visit may be beyond the end of the Analysis Period, as long as the onset is prior to the end of the Analysis Period.

* Note: In the extension study, visits are scheduled with a time window of +/- 14 days for conducting the EDSS assessment, the minimum per-protocol allowed time difference between two EDSS assessments scheduled 24 weeks apart is 140 days (24 weeks = 168 days minus a 14-day visit time window for each of the 2 visits, i.e., 168 days - 28 days = 140 days).

If an EDSS increase cannot be confirmed due to no available EDSS assessment, but the subject dies due to MS (death with reason 'Multiple sclerosis') the CDA is also considered confirmed, with confirmation date being the death date and onset date of the initial EDSS increase.

- 3. If a confirmation visit cannot be found in step 2, then steps 1 and 2 are repeated to look for the next disability accumulation onset and its confirmation visit. If a confirmation visit is found in step 2, then the algorithm stops for this subject, otherwise steps 1 and 2 are repeated until the last disability accumulation onset is assessed.
- 4. If at none of the assessments a 24-week CDA is identified, but the subject dies due to MS (experiences a relapse with outcome death) the subject is considered to have a 24-week CDA with onset date being the death date.
- 5. Event status and time to event variables for time to event analyses:

After steps 1, 2, 3 and 4 are performed, a subject is considered to have a 24-week confirmed disability accumulation if an accumulation onset with a confirmation visit is found. Otherwise, the subject is considered not to have a 24-week confirmed disability accumulation and is referred to as a censored subject.

For subjects with a 24-week confirmed disability accumulation, the time to event variable (days) is calculated as (onset date – date of first treatment with ponesimod + 1). The onset date is based on the EDSS assessment date rather than the associated nominal visit date.

For subjects without a 24-week confirmed disability accumulation, their time to event variable is calculated as (censoring date – date of first treatment with ponesimod + 1).

Censoring

The censoring date is defined as: Date of last EDSS assessment without an EDSS increase. Subjects without post baseline assessment (without EDSS increase) are censored on ponesimod

CONFIDENTIAL – FOIA Exemptions Apply in U.S.

start date. Time to censoring is defined as censoring date minus date of date of first treatment with ponesimod + 1.

For handling of missing dates see Section 6.14.

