EDSS increase of 0.5 point or 1-point increase in 1 to 3 FS*	EDSS increase of 1 or 2 points or 2-point increase in 1 or 2 FS* or 1-point increase in 4 or more FS*	Exceeding moderate relapse criteria: EDSS increase of 2.5 points or 2-point increase in 3 FS* or 3-point increase in 1 FS* or 2-point increase in more than 2 FS*

Table 7:Severity of relapse

* excluding the bowel and bladder, and mental FS.

Note: The EDSS increase is the increase observed at the EDSS assessment associated with the relapse, as compared the preceding EDSS assessment (performed prior to the relapse).

3. Time to 24-week confirmed disability progression up to end of the study.

Disability progression is defined as an increase of at least one full point in the EDSS score (or 1.5 points if the baseline EDSS was 0, or 0.5 points if the baseline EDSS was equal or greater than 5.5) with or without relapse, confirmed at the next scheduled EDSS assessment at least 24 weeks later (or if missing, at the next available scheduled EDSS assessment). The time to event is defined as the time from initiation of study treatment until the first EDSS assessment meeting the criteria for disability progression.

- 4. Other relapse-related endpoints:
 - Annualized total relapse rate.
 - Time to first (total) relapse.
 - Number of (confirmed and total) relapses.
 - Number of patients without any (confirmed and total) relapse.
 - Number of patients with a relapse requiring corticosteroid treatment.
- 5. MRI-related endpoints:

Confidential

EudraCT 2009-011470-15 EDMS-ERI-206617631

- Number of Gd+ lesions per patient recorded on T₁-weighted MRI scans at all assessments.
- Number of patients with no Gd+ lesions on T₁-weighted MRI scans at all assessments.
- Total volume of Gd+ lesions per patient on T₁-weighted MRI scans at all assessments.
- Number of new or enlarging lesions per patient on T₂-weighted MRI scans at all assessments.
- Change from baseline to all assessments in total lesion volume per patient on T₂-weighted MRI scans.
- Number of combined unique active lesions (Gd+ lesions plus new or enlarging T₂ lesions without gadolinium-enhancement) per patient on MRI scans at all assessments.
- Percentage change of brain volume from Visit 2 (from AC-058B201) up to the end of the study.
- Percentage change of brain volume from Visit 11 (from AC-058B201) up to the end of the study.
- 6. Neurological endpoints:

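### SAP 5.3.5.1 applies the 140-day tolerance for 24-week disability accumulation to visit pairs outside the schedule that justifies it

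*SAP*

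**What the plan says.** Protocol 3.10.1 counts a progression only if it is "confirmed at the next scheduled EDSS assessment at least 24 weeks later". If that assessment is missing, the next available scheduled one is used, which is later and not earlier.

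SAP 5.3.5.1 defines the event as an increase sustained for 24 weeks: "every EDSS score (scheduled or unscheduled, with or without relapse) within a 24-week duration after the first accumulation should meet the accumulation criteria". The algorithm then works as follows.

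- **Onset (step 1):** "All available post-baseline EDSS assessments (scheduled or unscheduled, with or without relapse) are compared to the baseline EDSS". An unscheduled relapse visit can therefore start an event.
- **Confirmation (step 2):** "As a general rule, disability accumulation can only be confirmed at a scheduled visit and in the absence of a relapse". The SAP widens what counts as scheduled: "Note that the EOS/early discontinuation visit and the follow-up visit (in core, TP1, TP2, and TP3) are protocol specified visits", and they may confirm. The interval condition is "This visit is ≥ 24 weeks (140* days) from the potential onset date". All scores between onset and this visit must meet the criterion.
- **Basis for 140 days (note to step 2):** "the minimum per-protocol allowed time difference between two EDSS assessments scheduled 24 weeks apart is 140 days", obtained as "24 weeks = 168 days minus a 14-day visit time window for each of the 2 visits".

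No other threshold is given for unscheduled onsets or for confirmation at visits timed from the last dose. SAP 6.2 does not list the 140-day figure. Its only row on the confirmation rule itself concerns relapses with a missing end date (90 days instead of 30).

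**The concern.** The tolerance allows for two scheduled visits that each drift within their window. An unscheduled relapse EDSS has no window and no partner visit planned 24 weeks later, so there is no drift to allow for. An early-discontinuation or follow-up visit is timed from the last dose, not from the 24-week grid, and the follow-up windows are narrower than ±14 days. For these pairs the 28-day allowance has no stated basis, and an increase observed for 20 to just under 24 weeks can carry the 24-week label. At stake are the CDA event rate, the Kaplan-Meier curves and the match between the endpoint's name and its derivation.

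**Working it through.** **1. The plan's own figure.** 24 × 7 = 168 days; 168 − 2 × 14 = 140 days; 140 / 7 = 20.0 weeks. It reproduces.

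**2. Does 140 days work for regular pairs?** Yes. Two visits 12 weeks apart are at most 84 + 28 = 112 days apart, so 140 days separates them cleanly from 24-week pairs. A blanket 168-day rule would be too strict: with both visit dates uniform within ±14 days, about 50% of regular 24-week pairs fall below 168 days.

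**3. Unscheduled onset in TP2/TP3.** EDSS is done at every visit, 12 weeks (84 days) apart (Protocol 3.1.1, 3.11.1.3). Let the onset fall u days after a scheduled visit, 0 < u < 84, with u uniform (an assumption). Later visits come 84 − u, 168 − u and 252 − u days after onset.

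- 168 − u ≥ 140 requires u ≤ 28, so the share with a first eligible visit below 168 days is 28/84 = 33%. The median interval is about 154 days.
- Simulated visit shifts of 0, ±7 and ±14 days give 33.4%, 33.5% and 33.5%.
- Under a 168-day minimum these onsets would be confirmed at 252 − u = 224 to 252 days without shifts, median about 238.

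**4. Unscheduled onset in TP1, weeks 0–48.** EDSS is at Weeks 24 and 48, so the spacing is 168 days. The share is 28/168 = 17%; with ±14-day shifts it is 16.7% for onsets in weeks 0–24 and 14.5% for weeks 24–48. For an affected onset in weeks 0–24, a 168-day minimum moves confirmation to 336 − u = 308 to 336 days.

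**5. Confirmation at a follow-up visit.** FU2 is 30 days (±5) and FU3 is 90 days (±7) after the last dose. Suppose onset is at a regular visit k days before the last dose.

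- FU3: 140 ≤ k + 90 ≤ 167 gives k = 50 to 77.
- FU2: 140 ≤ k + 30 ≤ 167 gives k = 110 to 137.

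Such pairs were never planned 24 weeks apart. Their combined windows are 14 + 7 = 21 or 14 + 5 = 19 days, not 28.

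**6. On-schedule end of treatment.** EOT3 at Week 540 has a ±14-day window and lies 540 − 516 = 24 weeks after P44, which also has ±14 days. The note's argument covers this pair. EOT2 at Week 96 lies 96 − 48 = 48 weeks after E9, so either threshold is met.

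**7. Direction.** An onset confirmed at 168 days or later, with all intervening scores qualifying, also passes at 140 days. Onsets are tried in order of date. The 140-day rule can therefore add events or move onset earlier, but cannot remove or delay one.

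**The case against.** The safeguards are real. An unscheduled visit can start an event but cannot confirm it. Confirmation must fall outside a relapse, and every intervening score must qualify. For the TP2/TP3 onsets in item 3 this includes a scheduled visit at about 84 − u = 56 to 84 days. So a 20-week worsening can be counted; it is not counted automatically.

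A reader might also infer that recovery between weeks 20 and 24 is being overlooked. On the regular TP2/TP3 grid there is usually nothing to overlook: after confirmation at 140 days or later, the next regular visit is at least 84 − 28 = 56 days on, at day 196 or beyond. Only an unscheduled, EOT or follow-up EDSS could fall before day 168. The documents give no figure for recovery in that interval.

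Event time is the onset date, so an onset that is still confirmed later leaves the curves unchanged. Protocol 1.3.2.3 reports an adjusted relapse rate of about 0.15 per year at 20 mg, so relapse visits are infrequent. The threshold and its arithmetic are printed in the endpoint section, so the missing row in SAP 6.2 is a matter of record-keeping.

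All of this stands and limits the size of the problem. It does not supply a basis for 140 days where one visit of the pair is off schedule.

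**Conclusion.** The point holds in limited form. The 140-day minimum is sound for regular on-schedule pairs. Applied to unscheduled onsets and off-schedule confirmations, it lets 140–167 days count as 24 weeks, against the protocol and the SAP's own definition.

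The one-third and one-sixth figures assume uniformly timed unscheduled onsets and describe when the first eligible visit falls. A reader might take them as the share of CDA events that are false. The documents do not support that: they give no count of relapse-visit onsets, and many such onsets would fail the other conditions or be confirmed later from the same date. The number of events affected is unknown and probably small.

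Nor do the documents show a bias in the hazard ratios. The rule is the same in every dose group, all objectives are exploratory, and p-values have been removed. The consequence is for the event rate and the 24-week label, not for a formal test.

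**What to change.** In SAP 5.3.5.1 step 2:

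- Keep 140 days when onset and confirmation are both regular on-schedule visits nominally at least 24 weeks apart, including an on-schedule EOT2 (Week 96) or EOT3 (Week 540).
- Require at least 168 days when onset is an unscheduled EDSS, or when confirmation is an off-schedule early-discontinuation EOT, EOS or follow-up visit.
- Record the 140-day tolerance and its scope in SAP 6.2 as a departure from the protocol's 24-week minimum.

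The cost is a few lines of text and one condition in the derivation. A few events will be confirmed later, in TP2/TP3 typically at about 238 days, which is further from 24 weeks than now but in line with the protocol. Patients with no later eligible visit lose the event and are censored under the existing rule, at their last EDSS showing no increase.
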